This Phase 3b multicenter, randomized, open-label study will enroll subjects with relapsed/refractory follicular lymphoma grades 1-3b, transformed follicular lymphoma, marginal zone lymphoma or mantle cell lymphoma. All subjects enrolled will receive 12 cycles of lenalidomide plus rituximab induction therapy.

The study is designed to compare the efficacy and safety of two maintenance regimens following the induction therapy. Subjects who have stable disease (SD), partial response (PR), unconfirmed complete response (CRu) or complete response (CR) at the end of 12 cycles of induction therapy will be randomized to one of two maintenance arms: Arm A (experimental) or Arm B (control). Subjects randomized to Arm A will receive lenalidomide plus rituximab combination maintenance therapy (for 18 cycles) followed by optional lenalidomide single-agent maintenance (to progression). Subjects randomized to Arm B will receive rituximab single-agent maintenance (for 18 cycles).

Subjects will be stratified at time of randomization to the maintenance arm by histology, lines of anti-lymphoma therapy, and age.

The overall study design is described in Figure 1. The study is divided into a Screening Period, a Treatment Period (induction and maintenance), and a Follow-up Period. Approximately 500 subjects are planned to be enrolled.

Upon giving written informed consent, a subject will enter the Screening Period and undergo safety and other assessments to determine eligibility for the study. All Screening assessments must be completed within 28 days prior to the subject initiating induction therapy.

Subjects enter the Induction Treatment Period at the time they complete screening procedures and meet all eligibility criteria. Eligible subjects entering the Induction Treatment Phase will be enrolled using an Interactive Voice Response System (IVRS). The treatments will be given as described in detail in Section 8 and must begin no later than 1 week after enrollment in IVRS to receive induction therapy. Cycle length during induction and maintenance is 28 days.

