5 TABLE OF EVENTS

		E				Induc	tion Pe	riod			Maintena nce Period	At 3 cycles (84 days after		Follo	ow-up	
PROCEDURE ^a	Screening Period	Every Cycle Day 1 Induction & Maintenance Periods (± 3 days)	C	ycle 1	l	Cycles 2 & 3	Cycles 3, 5, 7, 9 & 11	Cycles 5 & 9	Cycle 7	Cycle 10	Cycles 13, 15, 17, 19, 21, 23, 25, 27 & 29	At 6 cycles (168 days after C1D1)(±2 weeks)		If no PD then follow the CT		Ŧ
	Days -28 to -1	Up to PD for Arm A Or up to 30 cycles for Arm B	Day 1 (± 3 days)	Day 8 & 15 (± 1 day)	Day 22	Day 15 (± 1 day)	Day 1	Day 1 (± 3 days)	Day 1 (± 3 days)	Day 1 (± 3 days)	Day 1 (± 3 days)	Every 6 cycles (168 days) (±2 weeks) up to 5 years then Annually (± 3 weeks) ^b	At Treatment Discontinu ation/ Completio n	scan assessment schedule ^b		
Informed Consent	Х	-	-	-	-	-	-	-	-	-	-	-	-	-	-	
Inclusion/Exclusion Criteria	X	-	-	-	-	-	-	-	-	-	-	-	-	-	-	-
Demographic Data	Х	-	-	-	-	-	-	-	-	-	-	-	-	-	-	-
Lymphoma and Complete Medical History	х	-	-	-	-	-	-	-	-	-	-	-	-	-	-	-
Central Nervous System Lymphoma Evaluation	х	-	-	-	-	-	-	-	-	-	-	-	-	-	-	-
Creatinine Clearance (Cockcroft-Gault Estimation)	х	-	-	-	-	-	-	-	-	-	-	-	-	-	-	-
12-Lead Electrocardiogram	Х	-	-	-	-	-	-	-	-	-	-	-	-	-	-	-
HBV Screening ^c	Х	-	-	-	-	-	-	-	-	-	-	-	-	-	-	-

		E				Induc	tion Pe	riod			Maintena nce Period	At 3 cycles (84 days after		Follo	ow-up	
PROCEDURE ^a	Screening Period	Cycle Day 1 Induction & Maintenance Periods (± 3 days)		Cycle 1	L	Cycles 2 & 3	Cycles 3, 5, 7, 9 & 11	Cycles 5 & 9	Cycle 7	Cycle 10	Cycles 13, 15, 17, 19, 21, 23, 25, 27 & 29	At 6 cycles (168 days after C1D1)(±2 weeks)		If no PD then follow the CT		Ŧ
	Days -28 to -1	Up to PD for Arm A Or up to 30 cycles for Arm B	Day 1 (± 3 days)	Day 8 & 15 (± 1 day)	Day 22	Day 15 (± 1 day)	Day 1	Day 1 (± 3 days)	Day 1 (± 3 days)	Day 1 (± 3 days)	Day 1 (± 3 days)	Every 6 cycles (168 days) (±2 weeks) up to 5 years then Annually (± 3 weeks) ^b	At Treatment Discontinu ation/ Completio n	scan assessment schedule ^b		
Eastern Cooperative Oncology Group (ECOG) Performance Status	X	-	-	-	_	-	-	-	-	-	-	-	X	-	-	-
B Symptoms	Х	-	-	-	-	-	-	-	-	-	-	-	Х	-	-	-
Vitals Signs	X	X	-	-	-	-	-	-	-	-	-	-	X	-	-	-
Hematology Laboratory Tests ^g	X	Х	-	x	-	X	-	-	-	-	-	-	Х	-	-	-
Serum Chemistry Laboratory Tests ^g	X	Х	-	x	-	X	-	-	-	-	-	-	X	-	-	-
Thyroid Stimulating Hormone ^{g,n} (TSH)	X	-	-	-	-	-	-	-	-	-	-	-	х	-	-	-
Tumor Flare and Tumor Lysis Assessments ^h	-	-	X	x	-	-	-	-	-	-	-	-	-	-	-	-

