6.3 Efficacy Assessments

Radiological assessments for efficacy will be CT scan or MRI, to confirm the presence of measurable disease of > 1.5 cm in the transverse diameter at baseline. A CT is to be performed with contrast unless it is medically contraindicated. The regions to be imaged can be the neck, chest, and abdomen/pelvis, as well as any other regions clinically indicated for tumor imaging. The same imaging modality and regions for lesion evaluation at Screening must be consistently used throughout the study. CT/MRI scan performed for the purpose of standard of care may be used as the Screening CT scan if it is obtained within 8 weeks prior to C1D1.

All CT or MRI scan assessments will be determined from first dose date and will follow the counting of the dosing Cycles (ie, 1 cycle = 28 days). It is critical that the same modality used at Screening be used throughout the study for each subject. The scans must be performed:

- At 3 cycles after C1D1 (84 days \pm 2 weeks)
- At 6 cycles after C1D1 (168 days \pm 2 weeks)
- then every 6 cycles (168 days \pm 2 weeks) for 5 years
- and annually (± 3 weeks) thereafter until disease progression, relapse, or initiation of new antilymphoma therapy
- After the confirmation of the 114 PFS events, no efficacy assessments will be conducted

A subject with positive bone marrow at Screening will have a repeat bone marrow biopsy to confirm radiological CR only if the subject has otherwise fulfilled the criteria for a nodal CR; this bone marrow biopsy should be performed within 28 days after the criteria for CR have otherwise been met.

In addition to CT/MRI scan to assess disease, subjects with MZL involving the gastric area will undergo endoscopy as part of the response assessment. Subjects will have a repeat gastric biopsy for histological evaluation if the subject has fulfilled the IWG criteria for response of at least a CR/CRu. Histological evaluation will be performed by local pathologies laboratories using the GELA grading system (Copie-Bergman, 2003; Copie-Bergman, 2012; see also Section 6.1.6).

All enrolled subjects are followed for PD or relapse using the schedule described in Table 1.This includes subjects who discontinue treatment for any reason without documented evidence of PD or relapse. Subjects who start a new anti-lymphoma therapy without evidence of PD or relapse will not be followed by radiological assessments.

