8.2.4.2 Dose Modification or Interruption for Lenalidomide

The dose of lenalidomide for each subject will be interrupted and modified following toxicity as described in Table 2. Refer to Table 3 and Table 4 (and Table 5 for the maintenance period) for dose reduction instructions for study drug; the dose may also be reduced for reasons in addition to those listed in Table 2 per investigator discretion. If a dose is reduced, re-escalation is not permitted unless discussed with Celgene Medical Monitor.

If a subject experiences an AE that requires a dose interruption, the subject cannot be re-started on study drug until the AE has resolved or reached acceptable grade as described in Table 2. Once the AE has resolved, the subject may restart study drug (at the dose level required in Table 2, and refer to Table 3 and Table 4 [and Table 5 for the maintenance period] for the actual dose) for the

remainder of the Cycle. Doses that were missed, because of toxicity or any other reason, will not be rescheduled.

If the start of the next Cycle is delayed due to an AE, the subject can re-start study drug for that next Cycle once the AE has resolved and the requirements detailed below have been met.

The new Cycle of treatment may begin on the scheduled Day 1 of the next Cycle once a 7-day rest period has occurred and if:

- The ANC is \geq 1,000 cells/mm³ (1.0 x 10⁹/L).
- The platelet count is $\geq 50,000 \text{ cells/mm}^3 (50 \times 10^9/\text{L})$.
- Lenalidomide-related allergic reaction or hypersensitivity not requiring discontinuation has resolved to ≤ Grade 1 severity.
- Any other lenalidomide-related AE not requiring discontinuation has resolved to ≤ Grade 2 severity.

If these conditions are not met on Day 1 of a new Cycle, the subject will be evaluated at least once every seven days and a new Cycle of study drug will not be initiated until the toxicity has resolved as described above. If a new Cycle is delayed for more than 28 consecutive days (counting begins following the mandatory 7-day rest period), the Medical Monitor must be notified. The treatment can be resumed according to the treating physician and could be discussed with the Medical Monitor.

The study assessments should remain in line with dosing days (the actual number of days that lenalidomide plus rituximab has been administered) but the tumor assessments will be determined from C1D1 and will follow the counting of the dosing Cycles, ie, 28-day cycles.

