8.3 Method of Treatment Assignment

Enrollment into the Induction Treatment Period will occur in the Screening Period, once all the required Screening procedures have been completed and subject meets all eligibility criteria, and all required data have been submitted to the IVRS/ Interactive Web Response System (IWRS) system. Upon completion of 12 cycles of induction therapy and achieving a response of PR or CR/CRu or having SD, the maintenance treatment will be randomly assigned using the IVRS. Subjects randomized under previous protocol (version 16 January 2014) who achieve a response of SD or better at the end of the Induction Treatment Period will remain in their originally assigned arm of maintenance therapy.

- Subjects will undergo randomization in a 1:1 ratio to either Arm A (maintenance therapy as rituximab plus lenalidomide followed by optional lenalidomide) or Arm B (maintenance therapy as rituximab). The randomization procedure will be accomplished by a validated interactive voice response system (IVRS/IWRS).
- Randomized subjects will be stratified by:
 - Histology (FL (grades 1-3b and transformed FL) versus MZL versus MCL)
 - Lines of anti-lymphoma therapy ($\leq 2 \text{ vs.} > 2 \text{ lines}$)
 - Age (< 65 vs. \geq 65 years)

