Duration of response is defined only for subjects who have achieved PR or better after the first dose date of maintenance therapy and prior to any treatment change. It is calculated as the time from the initial response (at least PR) after the first dose date of maintenance therapy and prior to treatment change to documented disease progression or death.

Subjects who have not progressed or died at the time of the clinical data cutoff date will be censored at the last assessment showing no progression. Subjects who change treatment without evidence of disease progression will be censored at the last assessment showing no progression prior to treatment change.

Duration of Complete Response

Duration of complete response is defined only for subjects who have achieved CR/CRu after the first dose date of maintenance therapy and prior to any treatment change. It is calculated as the

time from the initial response (at least CRu) after the first dose date of maintenance therapy and prior to treatment change to documented disease progression or death.

Subjects who have not progressed or died at the time of the clinical data cutoff date will be censored at the last assessment showing no progression. Subjects who change treatment without evidence of disease progression will be censored at the last assessment showing no progression prior to treatment change.

Time to Next Anti-lymphoma Treatment

Time to next anti-lymphoma treatment is defined as the time from the first dose date of maintenance therapy to the time of first documented administration of new anti-lymphoma therapy. Subjects without new treatment therapy will be censored at the last visit.

Time to Histological Transformation

Time to histological transformation is defined as the time from the first dose date of maintenance therapy to the time of histological transformation as measured based on documentation of histological transformation (as assessed by the investigator). In case of clinical suspicion of transformation, including rapid disease progression, unexpected changes in "B" symptoms or rapidly increasing LDH, a biopsy should be performed. In this clinical trial, histological transformation will be considered disease progression. This endpoint will not be calculated for subjects randomized with transformed Follicular Lymphoma (tFL).

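### DOR and DOCR start at the first response documented after maintenance begins, so existing responders start about 24 weeks late, early failures drop out, and the arms are compared on a subset selected after randomization.

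*Combined protocol and SAP*

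**What the plan says.** Randomization to maintenance follows induction (Section 8.3): "Upon completion of 12 cycles of induction therapy and achieving a response of PR or CR/CRu or having SD". Subjects therefore enter the comparison in CR/CRu, PR or SD.

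Section 10.6.2 fixes both the DOR subset and its clock. On the subset: "Duration of response is defined only for subjects who have achieved PR or better after the first dose date of maintenance therapy". The clock is the "time from the initial response (at least PR) after the first dose date of maintenance therapy", ending at progression or death. For DOCR the clock is the "time from the initial response (at least CRu) after the first dose date of maintenance therapy". No rule says how to date a response that was already present at randomization.

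Scans run on the induction clock. Section 6.3 says "All CT or MRI scan assessments will be determined from first dose date", and Section 8.2.4.2 says "the tumor assessments will be determined from C1D1 and will follow the counting of the dosing Cycles, ie, 28-day cycles". After scans at 3 and 6 cycles, Table 1 has them "Every 6 cycles (168 days) (±2 weeks) up to 5 years then Annually".

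Section 2.2 lists DOR and DOCR among the endpoints on which the arms are to be compared. Section 10.6.4 applies the stratified log-rank test, with a rule for declaring the experimental arm superior, to the time-to-event endpoints as a class. By contrast, PFS, OS, time to next treatment and time to transformation all start at the first maintenance dose.

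**The concern.** In most trials response comes after randomization, so some conditioning on response is unavoidable in DOR. Here many responses come before it. A responder set fixed at baseline is available, but the plan re-selects responders on what is seen during maintenance.

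Two things follow for a subject already in PR or better. The time between the first maintenance dose and the first maintenance scan is not counted. And a subject who fails in that interval contributes no DOR at all, although this is the kind of outcome maintenance is meant to prevent.

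At stake is how a comparative secondary endpoint is read. Section 4.2 gives longer response as an expected benefit of longer lenalidomide. The reported figure would be neither total response duration nor duration from randomization. If maintenance affects early failure, the two DOR subsets would also differ in composition by arm.

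**Working it through.** The plan gives no figure for DOR or DOCR, so there is none to reproduce. Its projection of 114 PFS events at 105 months (Section 10.3) is used below to calibrate the early event rate.

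**1. When the clock starts**
- The Protocol Summary states: "Cycle length during induction and maintenance is 28 days". Induction is 12 × 28 = 336 days, so maintenance starts at about day 336.
- Scheduled scans fall on days 84, 168, 336, 504, and so on. The first scan after the start of maintenance is day 504.
- Gap: 504 − 336 = 168 days, or 24 weeks (22 to 26 weeks with the ±2-week window).
- A late start shortens the gap, because scans stay on the first-dose clock: 20 weeks after a 28-day delay, 12 weeks after an 84-day delay.

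**2. Who is excluded**
A subject in PR at day 336 who progresses or dies by the day-504 scan has no scheduled assessment showing PR after the first maintenance dose. That subject fails the entry condition for DOR. The same holds for CR/CRu and DOCR.

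**3. How many**
The assumed median PFS values are redacted, so I solve for the pooled median M that matches the plan's own event projection.

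Inputs from Section 10.3: about 314 randomized (projected), 63 months of accrual, 5% annual dropout, 114 events at month 105. Assumptions: uniform accrual, 12-month induction, exponential PFS. Follow-up from the first maintenance dose then runs from 105 − 12 − 63 = 30 to 105 − 12 = 93 months.

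With λ = ln 2 / M and δ = −ln(0.95)/12 = 0.00427 per month:

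E = N × λ/(λ+δ) × {1 − [e^(−30(λ+δ)) − e^(−93(λ+δ))] / [63(λ+δ)]}

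At M = 78.8 months, λ = 0.00879, λ+δ = 0.01307 and λ/(λ+δ) = 0.673. The averaged exponential term is 0.460, so E = 314 × 0.673 × 0.540 ≈ 114.

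Share with an event in 168 days (168/30.4375 = 5.52 months): 1 − 0.5^(5.52/78.8) = 4.7%, about 15 of 314.

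| N | Annual dropout | Implied median (months) | Event within 168 days |
|---|---|---|---|
| 350 | 0% | 106 | 3.5% |
| 314 | 5% | 79 | 4.7% |
| 250 | 10% | 48.5 | 7.6% |

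These shares cover all dosed subjects, including those randomized with SD. The documents do not allow the share among existing responders to be computed.

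**4. Direction of bias**
An illustrative simulation used 3,000 trials of 157 per arm, an unstratified log-rank test and a nominal 2.5% in each direction. Everyone event-free at 168 days entered DOR. Assumed: 35% of subjects have a median of 8 months and the rest 60 months, and Arm A multiplies the poor-prognosis hazard by 0.4 during the first 24 weeks only.

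| Scenario | DOR test favors A | DOR test favors B |
|---|---|---|
| No treatment effect | 2.6% | 2.1% |
| Early benefit in Arm A | 0.4% | 10.0% |

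In this scenario a real early benefit keeps poor-prognosis subjects in Arm A's DOR subset, and the comparison turns against Arm A. Other assumptions could give another direction.

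**The case against.** **The valid comparison already exists.** Primary PFS starts at the first maintenance dose and counts every early failure. For subjects already responding, a DOR with the same start is simply PFS in that subgroup. This is correct, and it is why the point is minor.

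**The superiority sentence is generic.** Section 10.3 requires superiority only on the primary endpoint, no alpha is allocated to DOR or DOCR, and the Amendment 5 rationale for revising the significance level refers to the primary analysis. This narrows the point, but Section 10.6.4 still exempts neither endpoint and Section 2.2 calls for a comparison. The statement in Section 10.6.2 ruling out formal testing sits in the OS paragraph and concerns only the period after the final primary analysis.

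**DOR may be meant for new responses only.** The text does not say so; it uses conversion language for improvement of response and not for DOR. If that was the intent, it also has to be written down.

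**The time shift is the same in both arms.** True: the shared scan schedule shortens the reported duration without itself favoring an arm. The problem for the comparison is the selection.

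**Stronger readings a reader might infer.**
- That 10% to 15% of subjects are lost. Medians of 36 and 24 months would give 10.1% and 14.7%, but with 314 subjects and 5% dropout they would also give about 191 and 231 events by month 105, against the 114 projected.
- That the clock is 420 days late, counting from a response at day 84 (504 − 84). That would credit time on induction treatment common to both arms; the shift that matters to a maintenance comparison is the 168 days.
- That the rule produces false claims of superiority. The simulation shows near-nominal rates with no effect and a bias against Arm A in the scenario tried.

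**Conclusion.** The point holds as a minor one. Followed as written, Section 10.6.2 gives a DOR and DOCR that omit about 168 days for subjects already in the relevant response, assuming no delay and no unscheduled scan. It also removes those who fail in that interval, so the between-arm test is not a randomized comparison.

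On the plan's own event projection, about 5% of all subjects (3.5% to 7.6%) have an event in that interval. This rests on uniform accrual, a 12-month induction, exponential PFS, 250 to 350 randomized and 0% to 10% annual dropout. The share among existing responders is unknown, the direction of any bias is not fixed, and primary PFS is unaffected.

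**What to change.** - State in Section 10.6.4 that between-arm DOR and DOCR results are descriptive and outside the superiority rule.
- In Section 10.6.2, for subjects in PR or better at the end of induction (CR/CRu for DOCR), include all of them and start the clock at the first maintenance dose. Say plainly that this is in effect PFS in a subgroup defined at baseline.
- Report subjects who convert later separately, from their first qualifying response. That group is still selected after randomization, which is a further reason to keep it descriptive.

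The cost is a few sentences and one changed derivation, using scan data already collected. The downside is that DOR and DOCR could no longer support a superiority claim.

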A pivotal event in the natural history of FL is histological transformation to more aggressive malignancies, most commonly diffuse large B-cell lymphoma (DLBCL). The reported frequency of higher grade FL transformation varies significantly, ranging from 10% to 60% of patients. Immunophenotypic and genetic features suggest that Grade 3b FL may be similar to de novo DLBCL, however, most clinical studies have not shown a survival difference between Grade 3a versus 3b FL. Transformation is defined as pathologically demonstrated and clonally confirmed progression of FL Grades 1, 2, 3a to DLBCL or other high grade morphology; progression from

FL Grades 1 and 2 to FL Grade 3a is not considered histologic transformation, but a common progression event during the course of therapy (Vaidyanathan, 2014).

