10.6.4 Analysis Methods

Time-to-Event Endpoints

For the time-to-event endpoints, the Kaplan-Meier estimates of the survival function will be calculated and graphically presented. The stratified log-rank test will be performed to evaluate treatment efficacy. The experimental arm will be declared superior if the 2-sided p-value from the stratified log-rank test is less than or equal to the desired significance level in favor of the experimental arm. The un-stratified log-rank test will be performed as sensitivity analysis.

Hazard ratio with two-sided 95% confidence interval (CI) will be estimated using the Cox proportional hazards model.

Binary Endpoints

The binary endpoints such as IOR will be summarized in frequency and percentage. The stratified Cochran-Mantel-Haenszel (CMH) test will be performed to evaluate treatment efficacy. The unstratified CMH test will be performed as sensitivity analysis.

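### TTNLT censors subjects who die untreated and is summarised by Kaplan-Meier, so the curve overstates the incidence of next treatment; TTHT has no censoring rule at all

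*Combined protocol and SAP*

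**What the plan says.** Section 10.6.2 measures TTNLT from the first maintenance dose "to the time of first documented administration of new anti-lymphoma therapy". Its one censoring sentence reads "Subjects without new treatment therapy will be censored at the last visit". Death is not named. By contrast, PFS (Section 10.6.1) and duration of response and of complete response (Section 10.6.2) count death as an event.

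TTHT, in the same section, runs from the first maintenance dose to investigator-documented transformation. It has no censoring sentence, so death, progression without transformation and new therapy are all unaddressed. The only subjects left out are those randomized with transformed FL.

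Section 10.6.4 states that for the time-to-event endpoints "the Kaplan-Meier estimates of the survival function will be calculated and graphically presented", with a stratified log-rank test and a Cox hazard ratio. It makes no exception for endpoints that exclude death, and no cumulative incidence or other competing-risk method appears in the text.

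On histology, the background in Section 1.1 says: "Transformation is defined as pathologically demonstrated and clonally confirmed progression of FL Grades 1, 2, 3a to DLBCL or other high grade morphology". Section 8.3 randomizes FL Grades 1 to 3b, transformed FL, MZL and MCL. Appendix E (Section 19.5.2) recognises transformation of gastric MALT lymphoma into DLBCL and classes it as progression.

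**The concern.** A subject who has died cannot start new therapy. Censoring at the last visit treats that subject as still able to start it, at the same rate as those who remain under observation. The Kaplan-Meier complement then describes a hypothetical population in which nobody dies untreated, and it exceeds the proportion who actually receive next treatment.

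Two things are at stake. A reader who takes a 5-year probability or a median from the TTNLT curve gets a figure that is too pessimistic about next treatment. The curve is also blind to deaths: two arms with the same rate of new therapy and different mortality have the same curve. The documents give some reason not to assume equal mortality. The placebo-controlled lenalidomide maintenance trial in DLBCL, summarised in Section 1.7, had a PFS hazard ratio of 0.708 but an OS hazard ratio of 1.218 (95% CI 0.861 to 1.721; P = 0.26). That OS result is not significant and does not forecast this trial.

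**Working it through.** The plan states no event rate, event count or power for TTNLT or TTHT, so it has no figure to reproduce.

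**Inputs.** All hazards are constant and annual, evaluated at 5 years.
- TTNLT event hazard a = 0.12: assumption.
- Death without the event, b = 0.03 or 0.06: assumption.
- TTHT event hazard a = 0.025: midpoint of the 2% to 3% per year given for FL in Section 1.1.

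**Formulas.**
- Kaplan-Meier complement: 1 − exp(−5a)
- Cumulative incidence of the event: a/(a+b) × [1 − exp(−5(a+b))]
- Composite of event or death: 1 − exp(−5(a+b))

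**TTNLT.**
- Kaplan-Meier complement: 1 − exp(−0.60) = 45.1%, whatever the death rate.
- b = 0.03: (0.12/0.15) × [1 − exp(−0.75)] = 0.800 × 0.528 = 42.2%.
- b = 0.06: (0.12/0.18) × [1 − exp(−0.90)] = 0.667 × 0.593 = 39.6%.
- Excess from unrounded values: 2.9 or 5.6 points.
- Death without new therapy: (0.03/0.15) × 0.528 = 10.6%, or (0.06/0.18) × 0.593 = 19.8%.
- Composite: 52.8% or 59.3%. Alive without new therapy: 47.2% or 40.7%.

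**Median TTNLT.** Kaplan-Meier gives ln 2/0.12 = 5.8 years. Cumulative incidence reaches 50% when exp(−0.15t) = 1 − 0.5/0.8 = 0.375, so t = 6.5 years, or when exp(−0.18t) = 1 − 0.5/0.667 = 0.25, so t = 7.7 years.

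**Range for TTNLT under other assumed rates, 5 years.**

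| Event hazard | 1 − KM | Cumulative incidence at death hazard 0.02 / 0.04 / 0.06 | Excess (points) |
|---|---|---|---|
| 0.05 | 22.1% | 21.1% / 20.1% / 19.2% | 1.0 to 2.9 |
| 0.10 | 39.3% | 37.6% / 36.0% / 34.4% | 1.7 to 4.9 |
| 0.15 | 52.8% | 50.5% / 48.4% / 46.4% | 2.2 to 6.3 |

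**TTHT, if deaths are censored.**
- Kaplan-Meier complement: 1 − exp(−0.125) = 11.8%.
- b = 0.03: (0.025/0.055) × [1 − exp(−0.275)] = 10.9%, an excess of 0.8 points (unrounded values).
- b = 0.06: (0.025/0.085) × [1 − exp(−0.425)] = 10.2%, an excess of 1.6 points.
- Over event rates of 2% to 3% and death rates of 2% to 6% per year, the excess is about 0.5 to 1.9 points.

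**Subjects not at risk of TTHT.** Section 10.3 puts MCL at about 10%. If none of those subjects could transform, the TTHT complement would be roughly 0.9 × 11.8% = 10.6%. This pulls the curve down, against the effect of censoring deaths.

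**The case against.** The strongest reply is that the treatment comparison is already sound. With deaths censored, the log-rank test compares cause-specific hazards and the Cox ratio is the cause-specific hazard ratio. Section 10.6.4 commits to a survival function and plans no TTNLT or TTHT probability at a fixed time. A mortality imbalance would also show in PFS and OS. All of this stands, so a reader who inferred that the TTNLT test or hazard ratio is invalid would go beyond the documents. What remains is the curve: it is planned, and readers take probabilities and medians from it.

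A second reply is that cumulative incidence alone does not cure the blindness to deaths. In the working, the arm with the higher death rate shows 39.6% next treatment against 42.2%, and so looks better. That is correct, and it is why the fix pairs the two curves or adds a composite.

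Three stronger readings of TTHT are tempting, and the documents support none of them.
- **That the plan censors deaths for TTHT.** It states no rule; the fault is an omission.
- **That the bias is much larger.** That needs progression or new therapy to act as competing events at higher rates, and the documents give neither the rule nor the rates.
- **That Section 1.1 obliges the sponsor to remove Grade 3b FL, MCL and MZL.** That definition is FL background, which Section 10.6.2 does not cite, and Appendix E recognises transformation in gastric MALT lymphoma. MCL is also its own randomization stratum, so if MCL subjects cannot transform they add nothing to the stratified log-rank test. The net direction of error in the TTHT curve is therefore uncertain.

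Finally, Section 4.4 mentions a Statistical Analysis Plan whose separate text is not in the supplied material. A rule there would answer part of this point.

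**Conclusion.** The point holds in limited form. On the wording of Sections 10.6.2 and 10.6.4, deaths without new therapy are censored for TTNLT, and one minus Kaplan-Meier overstates the cumulative incidence of next treatment. The direction follows from the method whenever such deaths occur. The size, 2.9 or 5.6 points at 5 years in the main illustration and 1.0 to 6.3 points over the tabulated range, rests on assumed constant hazards that the documents do not supply.

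For TTHT the finding is a missing censoring rule, with a smaller bias if deaths are censored. The histology question is one of passages to reconcile, not a demonstrated error. Both endpoints are secondary. The hypothesis tests, sample size, alpha and primary analysis are unaffected, so this is a desirable correction and not a critical one.

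**What to change.** 1. In Section 10.6.4, report TTNLT and TTHT by cumulative incidence with death as a competing event, and label the planned Cox ratio for both as cause-specific.
2. For TTNLT, show the cumulative incidence of death without new therapy beside that of next treatment, or add a sensitivity analysis that counts death as an event.
3. In Section 10.6.2, name death explicitly in the TTNLT rule. Give TTHT a rule covering death, progression without transformation and new therapy. Section 6.3 lists only TTNLT and survival as followed after progression, so the TTHT rule should say what happens then.
4. Reconcile the TTHT population in Section 10.6.2 with Section 1.1 and Appendix E, particularly for Grade 3b FL and MCL, without dropping MZL automatically.

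The cost is a few sentences and a little extra standard analysis on data already planned. Displayed incidences fall slightly under the cumulative incidence option; counting death as an event raises them, to 52.8% or 59.3% under the illustrative hazards.
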